7.2.9. Visit 6 - Follow-up 3/ End of Treatment phase (Day 56±3)

This visit will take place 56±3 days after the first injection. Participants will be interviewed by a physician, or his/her delegate, of the investigational clinical site about any changes in their medical status, concomitant medications AEs, AESI and SAE since the last visit.

The following assessment / activities will be performed during this visit

- Check if participant has met any individual halting rule
- Examination of the site of injection and assessment of local reaction.
- Record of demographics (*only weight and BMI*)
- A directed physical examination
- Record of vital signs in sitting or supine position*.
- Safety laboratory evaluations (blood and urine)
- Urine pregnancy test (For Females)
- A blood sample will be drawn for immunomonitoring analysis

* *Vital signs can be measured in sitting or supine position as well as long as within 1 patient the measurements are always done in the same position.*

During the visit, the Investigator may order one re-test of the following parameters: Demographics (Weight and BMI), vital signs (HR, RR, BP, body temperature), safety laboratory tests, urine pregnancy test (for females) if they need to evaluate the evolution of that parameter(s) or to confirm the value observed. The reason and results of this re-test will be documented in the participant's source data and in the eCRF.

At the end of the visit, the next visit (Visit 7) will be scheduled and confirmed with the participant.

7.2.10. Visit 7 – Long Term Follow-up 1 (Day 91±7)

This visit will take place 91±7 days after the first injection. Participants will be interviewed by a physician, or his/her delegate, of the investigational clinical site about any changes in their medical status, concomitant medications and/or occurrence of any AEs, AESI and SAE since the last visit and will be documented in participant's source data and in the eCRFs and assessed.

The following assessment / activities will be performed during this visit

- Check if participant has met any individual halting rule
- Record of vital signs in sitting or supine position*.
- Urine pregnancy test (For Females)
- A blood sample will be drawn for immunomonitoring analysis

* *Vital signs can be measured in sitting or supine position as well as long as within 1 patient the measurements are always done in the same position.*

During the visit, the Investigator may order one re-test of the following parameters: vital signs (HR, RR, BP, body temperature), urine pregnancy test (for females), if they need to evaluate the evolution of that parameter(s) or to confirm the value observed. The reason and results of this re-test will be documented in the participant's source data and in the eCRF.

At the end of the visit, the next visit (Visit 8) will be scheduled and confirmed with the participant.

7.2.11. Visit 8 – Long Term Follow-up 2 / End of Study (Day 210±14)

This visit will take place 210±14 days after the first injection. Participants will be interviewed by a physician, or his/her delegate, of the investigational clinical site about any changes in their medical status, concomitant medications and/or occurrence of any AEs, AESI and SAE since the last visit and will be documented in participant's source data and in the eCRFs and assessed.

The following assessment / activities will be performed during this visit

- A complete physical examination
- Record of vital signs in sitting or supine position*.
- Safety laboratory evaluations (blood and urine)
- Urine pregnancy test (For Females)

* *Vital signs can be measured in sitting or supine position as well as long as within 1 patient the measurements are always done in the same position.*

During the visit, the Investigator may order one re-test of the following parameters: vital signs (HR, RR, BP, body temperature), safety laboratory tests, if they need to evaluate the evolution of that parameter(s) or to confirm the value observed. The reason and results of this re-test will be documented in the participant's source data and in the eCRF.

7.2.12. Early Termination visit (ET)

Participants, who are withdrawn from the study (for any reason) or wish to stop (for any reason) his/her participation prematurely, will be invited to attend an Early Termination visit (ET).

If the withdrawn or study discontinuation occur between D0 (first vaccination) and D56 (28 days after the second vaccination), the subjects will be invited to perform the following assessment / activities during this Early termination visit:

- Examination of the site of injection and assessment of local reaction.
- Record of vital signs in sitting or supine position*
- Safety laboratory evaluations (blood and urine)

A blood sample could also be drawn for immunomonitoring analysis.

* *Vital signs can be measured in sitting or supine position as well as long as within 1 patient the measurements are always done in the same position.*

During the visit, the Investigator may order one re-test of the following parameters: vital signs (HR, RR, BP, body temperature), safety laboratory tests, if they need to evaluate the evolution of that parameter(s) or to confirm the value observed. The reason and results of this re-test will be documented in the participant's source data and in the eCRF.

If the withdrawn or study discontinuation occur after D56, participant will be asked to participate in a phone follow-up call at D91 and D210 for assessing occurrence of any AEs since the visit D56.

If the withdrawn or study discontinuation is related to an AE, the participant will be contacted by phone, at the discretion of the investigator, up to resolution or stabilization of the event. This will be documented in the participant's source data and in the eCRF.

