2.2. Outcomes

2.2.1. Primary outcome measures

- Rate of solicited Adverse Event up to 14 days after each injection.
- Rate of unsolicited AE up to 28 days after each injection.
- Rate of serious adverse events (SAEs) serious adverse reactions (SARs), suspected unexpected serious adverse reactions (SUSARs) and adverse events of special interest (AESI) all along the study period.

Safety and tolerability will be assessed after each vaccination and participants will remain under observation at the study site for at least one hour for presence of any acute reactions and solicited events and by means of a diary completed by the participants for 14 days after each vaccination (from day 0 up to day 14 and from day 28 up to day 42). For each AE/SAE/AESI, the intensity and the relationship to vaccination will be reported and will be evaluated by the investigator.

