4.5. Removal / Early Withdrawal

Participants are free to discontinue their participation in the study at any time, without prejudice and with any obligation to give his/her reason(s) and without any change in their treatment related to safety follow-up. The Investigator must withdraw any participant from the study if he/she requests to be withdrawn, or if it is determined that continuing would result in a significant safety risk or may affect the well-being of the participant.

³ https://www.cdc.gov/coronavirus/2019-ncov/need-extra-precautions/people-with-medical-conditions.html?CDC_AA_refVal=https%3A%2F%2Fwww.cdc.gov%2Fcoronavirus%2F2019-ncov%2Fneed-extra-precautions%2Fgroups-at-higher-risk.html

In addition, the participant may withdraw/be withdrawn for any of the following reasons:

- Administrative decision by the investigator / sponsor
- Ineligibility (identified at any time during the study) ‘in the case it is considered to be in the best interest of the subject’s health’
- Significant protocol deviation
- Non-compliance with study procedures/requirements
- Occurrence of an AE, which at the opinion of the investigator requires discontinuation of the participant or results in inability to continue to comply with study procedures/requirements
- Participant (Female) who become pregnant during the study
- Lost to follow-up

The reason for withdrawal, in case provided, will be recorded in the participant’s source data and in the e-CRF. If withdrawal is due to an AE, appropriate follow-up visits or medical care will be arranged, with the agreement of the participants, until the AE has resolved or stabilized.

In case of lost to follow-up, at least 2 contacts attempts must be made within 1 week to contact any participant lost to follow-up prior to the last scheduled visit. All attempted contacts (e.g. phone contact, post mail, email) will be documented in the participant’s source data.

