9.1.12.2. Recording of Adverse Events of special Interest (AESI)

A noteworthy event for the particular product or class of products that a sponsor may wish to monitor carefully. It could be serious or non-serious, and could include events that might be potential precursors or prodromes for more serious medical conditions in susceptible individuals.

In this study, the AESI for COVID-19 vaccine will be defined as:

[figure not shown]
- Acute respiratory distress syndrome (ARDS)
- Pneumonitis
- Acute cardiac injury
- Arrhythmia
- Septic shock-like syndrome
- Acute kidney injury
- Vasculitis
- Autoimmune disease (AID)
- Meningitis
- Atypical measles
- Anosmia
- Dysgeusia

The investigator should report all AESIs for the whole period of the study.

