9.1.12.3. Reporting of Serious (Expected or Unexpected) AEs

[figure not shown]
If the Investigator identifies a SAE or a SUSAR, it should be reported by the Principal Investigator to the sponsor without delay. The investigator should report all SAEs for the whole period of the study.

To proceed with notifying the sponsor of a serious adverse event, the investigator completes an initial notification form and immediately faxed or emailed it to SGS Medical Affairs.

Any fatal or life-threatening event should be reported immediately by phone or fax to the Sponsor. These preliminary reports will be followed within 24 hours by more detailed descriptions that will include a completed SAE form, as described below.

If the investigator is not capable of declaring the serious adverse events by the means listed above, they contact Institut Pasteur exclusively on the following number or email inbox:

For regulatory purposes, initial SAE reports should be submitted to the Sponsor immediately and should include:

- a suspected investigational medicinal product
- an identifiable subject (e.g., study subject code number)
- an adverse event with a seriousness and the Investigator's assessment of the relationship to study drug
- an identifiable reporting source (investigator contact details)

Once faxed or emailed, the printed SAE form and accompanying documentation should be placed in the SAE section of the Investigator's site file.

The sponsor responsibility is to assess the relationship with the study vaccine and the expectedness of the reported serious adverse event.

Since healthy volunteers are considered in this study, the sponsor should report immediately:

- Any deaths, life threatening event,
- SAE and SUSARs including event of medical importance
- Serious safety-related protocol deviations

to Competent Authorities, Ethics committees, Eudravigilance registry, and inform the investigators of all study site.

The clock starts at the time a sponsor representative is formally informed and confirmed the receipt of the report. The report to Competent Authorities, Ethics committees Eudravigilance registry (EVCTM) should be done, without delay, as soon as the following data have been ascertained:

- a suspected relationship with the investigational medicinal product
- an identifiable subject (e.g., study subject code number)
- an adverse event with a seriousness and the Investigator's assessment of the relationship to study vaccine

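### Day 91 and Day 210 safety calls are planned only for withdrawals after Day 56, so new SAEs and AESIs are not systematically sought in participants who leave earlier

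*Protocol*

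**What the plan says.** Section 7.2.12 of the protocol has three rules for participants who leave the study.

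- **Early leavers.** "If the withdrawn or study discontinuation occur between D0 (first vaccination) and D56 (28 days after the second vaccination"), they are invited to one visit with an injection-site check, vital signs and safety laboratory tests. An immunology blood sample is optional. No later contact is scheduled under this rule.
- **Late leavers.** "If the withdrawn or study discontinuation occur after D56, participant will be asked to participate in a phone follow-up call at D91 and D210". The calls ask about adverse events since the Day 56 visit.
- **AE-related leavers, whenever they leave.** "the participant will be contacted by phone, at the discretion of the investigator, up to resolution or stabilization of the event".

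Section 4.5 adds for AE-related withdrawal: "If withdrawal is due to an AE, appropriate follow-up visits or medical care will be arranged, with the agreement of the participants", again until the event has resolved or stabilized. Section 9.1.12.4 requires clinical follow-up of anyone who had an adverse event in the treatment period until the findings normalize, stabilize or are explained. It also provides for reporting of newly arising related SAEs.

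On the outcome side, section 2.2.1 makes the rates of SAEs, SARs, SUSARs and "adverse events of special interest (AESI) all along the study period" part of the primary outcome. Section 9.1.12.2 says "The investigator should report all AESIs for the whole period of the study", and section 9.1.12.3 says "The investigator should report all SAEs for the whole period of the study". The last visit is Visit 8 (section 7.2.11): "This visit will take place 210±14 days after the first injection". Under section 12.1 the safety analyses use the modified ITT population, which holds everyone who received at least one injection.

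**The concern.** The primary outcome and the collection rule cover different periods. The outcome runs to Day 210 for everyone injected. The rule that would deliver it after withdrawal applies only to the leavers with the least time left to observe. An early leaver with no recorded event counts in the denominator as event-free, although nobody was scheduled to ask.

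The listed AESIs include conditions such as autoimmune disease and vasculitis, which a single visit soon after withdrawal may precede. Section 1.5 discusses a theoretical risk of disease enhancement on later SARS-CoV-2 infection, and a visit held before any exposure cannot inform that. COVID-19 occurrence is also an exploratory outcome over the whole study (section 2.4).

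This cannot be left to a statistical analysis plan, because no analysis recovers data that were never sought. Withdrawals after randomization are not replaced (section 4.7), and each vaccine regimen has only 24 recipients, so one missed event is visible in a cohort rate.

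**Working it through.** The protocol states no withdrawal rate and no formal sample size calculation (section 12.6), so it has no figure of its own to reproduce. The check compares the rules and then sizes the gap.

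**Step 1: what is actively sought up to Day 210**

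| Participant | Scheduled or prescribed contact after leaving | New SAEs/AESIs sought to Day 210? |
|---|---|---|
| Leaves after Day 56 | Calls at Day 91 and Day 210 | Yes, if the person accepts |
| Leaves by Day 56, not AE-related | One visit | No |
| Leaves by Day 56, AE-related | One visit, then follow-up of that event until resolved or stable | Not systematically; contact is tied to the known event |
| Stops vaccination only (sections 4.8, 9.1.11) | All scheduled visits | Yes |

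**Step 2: days without scheduled contact.** Inputs are the Day 210 end of follow-up and the day of leaving *d*, taking the early termination visit to fall on day *d*. Share = (210 − *d*)/210.

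- *d* = 14: 196/210 = 93%
- *d* = 28: 182/210 = 87%
- *d* = 56: 154/210 = 73%

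A person who leaves on Day 57 and accepts the calls has no uncovered period. One day's difference in leaving therefore decides whether about 154 days are covered.

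**Step 3: follow-up time lost in one 24-person vaccine group.** The number of early leavers *k* is an assumption, shown for 1, 2 and 4. Total planned time is 24 × 210 = 5,040 person-days. Share lost = *k*(210 − *d*)/5,040.

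| *k* | Leave at Day 56 | Leave at Day 28 | Leave at Day 14 |
|---|---|---|---|
| 1 | 3.1% | 3.6% | 3.9% |
| 2 | 6.1% | 7.2% | 7.8% |
| 4 | 12.2% | 14.4% | 15.6% |

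**Step 4: what this can do to a cohort rate.** One event missed in 24 is 1/24 = 4.2 percentage points. If no event is observed and *k* leavers have unknown status to Day 210, the true proportion with an event lies between 0 and *k*/24: up to 4.2%, 8.3% or 16.7% for *k* = 1, 2 or 4. These are limits, not estimates.

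**Step 5: precision with zero events.** The two-sided 95% exact upper limit is 1 − 0.025^(1/*n*): 14.2% for *n* = 24, 14.8% for 23, 15.4% for 22 and 16.8% for 20. The chance of seeing at least one event at a true 5% rate, 1 − 0.95^*n*, is 70.8% for *n* = 24, 67.6% for 22 and 64.2% for 20. Dropping the leavers entirely overstates the loss, because each is observed until leaving. The effect on precision is modest; the main issue is unknown outcome status.

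**The case against.** The strongest counter-case is that the protocol already protects the people who matter most for safety. Much of this stands.

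- A reader might infer that early leavers have no later contact at all. The documents do not support that. AE-related leavers are followed for their event under sections 4.5, 7.2.12 and 9.1.12.4, and the last of these is mandatory.
- A reader might infer that data are missing exactly where safety-related withdrawal is likeliest. That is not supported either. Section 4.8 keeps participants with a serious adverse reaction, a related grade 3 or higher event or hypersensitivity in scheduled follow-up unless they are explicitly withdrawn. Section 9.1.11 does the same for COVID-19. The widest gap is for early leavers without an adverse event, where a link to the outcome is weakest.
- A reader might infer that the SAE/AESI rate is biased downward or that the arms are followed unequally. No withdrawal rate, overall or by arm, is given to show this.
- Section 9.1.12.4 sets a 30-day post-study SAE window that might be counted from the individual's early termination visit. The text counts from the last visit of the study, so a coverage figure built on the individual reading is not secure.

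There is also passive capture: the duty to report over the whole study, and an emergency card with a telephone number (section 7.2.2). Finally, people who withdraw may refuse contact.

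What does not stand is the conclusion that the gap is closed. Event-specific follow-up ends with the event. The late-reporting rule covers related SAEs only, omits non-serious AESIs and sets no active contact. A duty to report does not find events in someone nobody contacts. Refusal is no reason to ask late leavers and not early ones, and the protocol gives no rationale for the difference.

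**Conclusion.** The point holds in a limited form. Section 7.2.12 schedules Day 91 and Day 210 safety contact only for withdrawals after Day 56. New SAEs and AESIs up to Day 210 are therefore not systematically sought in injected participants who leave by Day 56, although they count in the denominator of a whole-study primary outcome.

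For an individual the gap is large, from about 73% to 93% of the 210 days for leaving between Day 56 and Day 14. For the trial its size is unknown, because it depends on the number of early leavers. The cohort figures above rest on assumed counts of 1, 2 and 4 of 24. The asymmetry in the text is certain; under-ascertainment is a risk and not a demonstrated bias. Participants who stop vaccination but remain in the study are outside this concern. The rule deserves correction because the loss is avoidable and falls on a primary outcome.

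**What to change.** In section 7.2.12, extend the existing Day 91 and Day 210 follow-up calls to every participant who received at least one injection, withdraws at any time and agrees to be called. The calls should ask about SAEs, AESIs and COVID-19 occurrence. For those leaving by Day 56 they come in addition to the early termination visit, and the recall period should start at that visit or the last contact instead of the Day 56 visit.

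The cost is at most two short calls per early leaver and one sentence in the protocol and the consent form. Some early leavers will decline, as some late leavers will. The sample size, the injections and clinical care do not change.

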7.2.13. Unscheduled Visit(s)

An unscheduled visit may be performed at any time during the study at the participant's request or as required by the Investigator due to medical considerations including suspicion or confirmed SARS-CoV-2 infection (see section 9.1.11).

A participant in contact, according to ECDC definition⁴, with a SARS-CoV-2 confirmed case or a participant with suspected or confirmed SARS-CoV-2 infection will be managed according to the following local procedure:

For the Belgium site:

If a participant notices a contact with a confirmed case or typical COVID-19 symptoms (see section 9.1.11) while he/she is present at CPU, an ad hoc nasal swabbing for a SARS-CoV-2 PCR will be performed. If the PCR result is negative, a physical examination, vital signs measurement (including body temperature, BP, HR, Oxygen saturation), will be performed. If the PCR result is positive, the General Practitioner (GP) will be contacted and contact with CPU staff will be limited.

If the contact with a confirmed case or symptoms are noticed at home, the CPU staff will advise the participant to get tested, within 3 days, at their GP and to send the result of the SARS-CoV-2 PCR to the investigator. If the participant is tested positive, he/she will be excluded from further visits at CPU for two weeks in order to prevent him/her contaminating the unit and he/she will be withdrawn from dosing (if applicable). A telephone follow-up will be organized with the participant up to 14 days after testing and further follow-up will be discussed with the GP. If no visits are planned two weeks after the positive PCR and if the subject is not hospitalized because of COVID-19, an unscheduled visit will be planned with the participant for a post-infection follow-up.

For the French site:

If a participant notices a contact with a confirmed case or experiences typical COVID-19 symptoms (see section 9.1.11) while he/she is present at CIC-Cochin-Pasteur, the following examinations will be performed: ad hoc physical examination, vital signs measurement (including body temperature, BP, HR, Oxygen saturation), nasal swabbing for SARS-CoV-2 PCR, blood samples for laboratory tests, including cell blood count, and ionogram with CRP. Blood culture will also be performed if body temperature is > 38°C. If the contact with a confirmed case or symptoms are noticed at home, the participant will be invited to attend an unscheduled visit within 3 days after notification of a contact with a confirmed case or onset of symptoms. The same tests as described above in case of contact or the subject notices the symptoms

⁴ <https://www.ecdc.europa.eu/sites/default/files/documents/Public-health-management-persons-contact-novel-coronavirus-cases-2020-03-31.pdf>

while at the site will be performed. In case of suspected severe forms, the participant will be sent to the ICU of the Cochin Teaching hospital where the recruiting center is affiliated.

The date and reason for the unscheduled visit will be recorded in the participant's source data and in the eCRF. AE monitoring and concomitant medication recording will be performed by the Investigator. Other procedures and evaluations will be completed as deemed necessary by the Investigator and may include (but not limited to) safety laboratory tests, vital signs and physical examination.

